Statistical analyses: We will analyze data on all randomized subjects with a baseline assessment and at least one post-baseline evaluation, using mixed effects models, described above. The mixed effects model method provides an estimate of the individual variability around the population trend, the variability of the individual intercepts (baseline values) and slopes (changes across time), and the correlation between them. A fully saturated treatment by time model will be utilized for inference. Covariance structure will be chosen based on Akaike's Information Criterion (AIC). Random group level treatment effects will also be evaluated for importance based on the model AIC. This method allows for any group level effects to be incorporated into the model. Denominator degrees of freedom will be calculated using the Kenward-Roger small sample correction.

Power Analysis: We used procedures described by Hedeker et al. (1999) for Random Regression Models for the proposed study to estimate needed sample size (the RMASS program provided by Hedeker). We estimated that with a final sample size of 78 (target n=98, with a drop-out rate of 20%), the study will have .80 power to yield a statistically significant result for a .72 effect size, accounting for Type I error correction, .5 correlation between time points, and one random effect in the model. We have previously found CCT-associated effect sizes of .72 for prospective memory functioning in Veterans with mild to moderate TBI (74% of whom had PTSD), as well as for the UPSA-B in individuals with severe mental illness. Although we have not previously used the WHODAS 2.0 to assess disability, we have also found CCT-associated effect sizes of .81-1.0 for quality of life in these populations. The trial was therefore powered to detect effect sizes in the .72 range.

H1b: Positive CCT-associated effects on community reintegration outcomes (housing stability, participation in employment/education, healthcare appointment attendance) will be detected at the end of the 1-year follow-up.

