Dependent variables: Proportion of months housed, proportion of months engaged in productive activity (work or school), and proportion of VA healthcare appointments attended during the 1-year follow up period (all three outcomes based on monthly data collected during the 1-year follow-up period). Any missing data on housing and work/school status will be accounted for by using a proportion based on the available data points. Healthcare appointment attendance will be gathered from CPRS data and will not be subject to missing data.

Independent variable: Treatment group (CCT vs education control).

Statistical analyses: ANOVA models comparing the treatment and control group on the three dependent variables above. We have selected ANOVA over alternative models (t-test; Wilcoxon Rank Sum; Poisson regression) due to the type of dependent variables (continuous) and the option to include any covariates that might be imbalanced between the treatment groups.

Power analysis: With 78 subjects (39 subjects per group), we will have .80 power to detect an effect size of .64, a medium-to-large effect size.

capacity, disability, and community reintegration.

Dependent variables: UPSA-B at 15 weeks, WHODAS 2.0 at 15 weeks, proportion of months housed, proportion of months engaged in productive activity (work or school), and proportion of VA healthcare appointments attended during the 1-year follow up period.

Independent variables: Treatment group (CCT vs education control).

Mediators: Cognitive improvement in GDS composite from 0-10 weeks (slope of change across weeks), improvement in CPSA cognitive strategy use from 0-10 weeks (slope of change across weeks).

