Statistical analyses: For this hypothesis, we will use the regression analytic strategy described by Krull and MacKinnon (1999, 2001). In this approach, four conditions must be met: a) a significant relationship between the independent variable (treatment group) and the dependent variables listed above, b) a significant relationship between the independent variable (treatment group) and the proposed mediators listed above, c) a significant relationship between the mediator and the dependent variables listed above, and d) the relationship between the independent variable (treatment group) and dependent variables listed above must be significantly lower after controlling for the proposed mediator. To test for significant mediation, we will conduct a Sobel test (Sobel, 1982). We will also use the formula provided by MacKinnon and Dwyer (1993) to determine the percentage of the intervention condition to primary outcome path that was accounted for by change in the mediator.

Power analysis: For the second hypothesis, we used the procedures defined by Fritz and MacKinnon (2007) for estimating sample sizes needed to achieve 80% power to detect the mediated effect. Similar to previous hypotheses, we have assumed a medium effect for the relationships between intervention condition and dependent variables and between mediators and our primary outcome. Using the Sobel test procedure described in our statistical analysis section above, we estimate that the proposed sample size would be sufficient to achieve 80% power to detect a mediated effect.

Exploratory Aim 3. Examine moderators of CCT effects.

Dependent variables: GDS composite, UPSA-B, WHODAS 2.0, proportion of months housed, proportion of months engaged in productive activity (work or school), and proportion of VA healthcare appointments attended during the 1-year follow up period.

Independent variable: Treatment group (CCT vs education control).

Moderators: Presence and severity of PTSD, depression, history of substance abuse, and TBI, duration of homelessness, baseline cognitive functioning (GDS composite)

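### The 80% power stated for mediation (H2) is for a Sobel test with unstated path sizes, not the four-condition rule the plan applies; at a medium effect that rule cannot reach 80% with 78 completers

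*Combined protocol and SAP*

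**What the plan says.** All of this is in Section 9, Analytic Plan and Power Analyses.

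- **H2, Power analysis.** The conclusion is that "we estimate that the proposed sample size would be sufficient to achieve 80% power to detect a mediated effect". On effect sizes it says only "we have assumed a medium effect for the relationships between intervention condition and dependent variables and between mediators and our primary outcome". The test powered is named: "Using the Sobel test procedure described in our statistical analysis section above". The sample size is given by reference, without a number. Alpha and sidedness are not given, and no size is named for treatment-to-mediator.
- **H2, Statistical analyses.** The decision rule is wider than the Sobel test: "In this approach, four conditions must be met: a) a significant relationship between the independent variable (treatment group) and the dependent variables listed above". The other conditions are a treatment-mediator relationship, a mediator-outcome relationship, and a significant fall in the treatment effect once the mediator is controlled.
- **Sample size elsewhere.** H1a is powered "with a final sample size of 78 (target n=98, with a drop-out rate of 20" per cent). Its paragraph ends: "The trial was therefore powered to detect effect sizes in the .72 range". H1b says: "With 78 subjects (39 subjects per group), we will have .80 power to detect an effect size of .64, a medium-to-large effect size".
- **Alpha elsewhere.** The Bonferroni sentence names H1a and H1b only.

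**The concern.** The mediated effect is the product of two paths: treatment-to-mediator (a) and mediator-to-outcome given treatment (b). The power statement gives a verbal size for b and for the total treatment-outcome effect, and nothing for a, so the 80% cannot be re-derived.

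The more basic difficulty is that the power statement and the decision rule concern different events. The statement is about the Sobel test. The rule also needs a significant total effect, and the plan's H1b paragraph shows that 78 subjects reach .80 for that test only at an effect it calls medium-to-large. An effect that is merely medium therefore cannot give 80% for the whole rule at that size.

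At stake is the reading of Aim 2. If readers believe the trial had 80% power, they will take a null H2 result as evidence against the proposed mechanism when a real mediated effect of medium size would often be missed.

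**Working it through.** **Inputs from the plan.** 98 randomised, 78 after 20% attrition (98 × 0.80 = 78.4), 39 per group. Effect sizes .64 (H1b) and .72 (H1a). Four-condition rule with Sobel test.

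**Assumptions, because the plan gives no figure.** Two-sided .05, no multiplicity correction, no covariates. Medium read as d=.50. The same d for treatment-to-mediator and for the total effect on the outcome. Path b between .30 and .50. Condition (d) is taken as the Sobel test, since in linear regression the fall in the treatment coefficient equals a × b.

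**Step 1: reproduce the plan's H1b figure.** For a two-sample t test with n per group, the noncentrality is d × √(n/2) on 2n − 2 degrees of freedom.

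- d=.64, n=39: .64 × √19.5 = 2.826, 76 df, power .797. This matches the stated .80, at unadjusted two-sided .05.

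The H2 figure of 80% cannot be reproduced in the same way, because its inputs are missing.

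**Step 2: the ceiling set by condition (a).** P(all four conditions) ≤ P(condition a).

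- d=.50, n=39: .50 × √19.5 = 2.208, power .587.
- d=.50, n=49 (all 98 retained): .50 × √24.5 = 2.475, power .688.

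This step does not use b. A total effect of .50 keeps the rule below 80% at either sample size, and at 78 any total effect below .64 does so.

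**Step 3: larger effects.** The Sobel statistic is z = ab / √(a²·se_b² + b²·se_a²). A hand check for N=78, d=.72, b=.39, with within-group SDs of 1:

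- se_a = √(1/39 + 1/39) = .2265
- se_b ≈ √((1 − .39²)/78) = .1043
- z ≈ (.72 × .39) / √(.72² × .1043² + .39² × .2265²) = .2808/.1159 = 2.42
- Normal approximation to power: Φ(2.42 − 1.96) = about .68

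The product of two estimates is not normal, so the figures below come from simulation (20,000 trials per main cell, ordinary least squares). Ranges cover different ways of scaling d and b (residual SD, within-group SD, full standardisation).

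| N | d | b | Sobel alone | All four conditions |
|---|---|---|---|---|
| 78 | .50 | .30 | 22-25% | 14-17% |
| 78 | .50 | .39 | 35-40% | 23-29% |
| 78 | .64 | .39 | 55-61% | 44-52% |
| 78 | .72 | .30 | 44-48% | 39-44% |
| 78 | .72 | .39 | 65-71% | 56-65% |
| 78 | .72 | .50 | 79-84% | 67-77% |
| 98 | .64 | .39 | 73-78% | 63-71% |
| 98 | .72 | .39 | 81-86% | 75-82% |

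**Step 4: sensitivity to the other unstated inputs.**

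- Treatment-to-mediator path, with N=78, total effect .72 and b=.39: Sobel (all four) is 22-27% (21-26%) if that path is .4, and 80-84% (68-75%) if it is .9.
- Alpha .025 with N=78, d=.72, b=.39 (within-group scaling): about 53% (46%).

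**The case against.** The strongest reply has four parts.

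*The percentages rest on a value of b that the plan does not give.* This stands. A reader might infer from the table that mediation power simply is 22-71%, or that 80% is wrong on every reading. The documents support neither. That range needs b between .30 and .39. With d=.72 and b=.50 the Sobel test reaches 79-84% at N=78. The full rule comes to about 80% at 78 with still larger paths: 76-85% at d=.78, b=.50, and 78-84% at d=.90, b=.39. The H1a paragraph does cite earlier effects of .81-1.0, but for quality of life, not for a mediator, and they are not medium.

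*The sample size is not absent, and 78 may be too low for some pairs.* This stands in part. The proposed sample size can be traced to 98 and 78 in other paragraphs, attrition may be lower among residents, and for one outcome "Healthcare appointment attendance will be gathered from CPRS data and will not be subject to missing data". Each pair still needs a 0-10 week mediator slope, however, and H1a and H1b are both powered at 78. Even 98 does not rescue a total effect of .50 (Step 2).

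*The .64 and .72 are not mediation assumptions.* True. They are the effects at which the plan powers other hypotheses, used here only because H2 names no number.

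*Causal steps with a Sobel test is a recognised, prespecified method.* Agreed. The objection here is to the power figure attached to it. Changing the criterion to joint significance or a bootstrap would be a trade-off, not a correction.

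**Conclusion.** The point holds in this form. The stated 80% does not describe the rule the plan will apply, and it cannot be derived from the inputs given.

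The firm part is the ceiling. It needs only the total effect, the sample size, and an unadjusted two-sided .05 test without covariates. Under the four-condition rule, a total effect below .64 cannot give 80% power at 78, whatever the mediator path.

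The conditional part is the size of the shortfall for larger effects, which turns on b, on the treatment-to-mediator path and on how many participants have data. In the cases examined, 80% for the full rule needs effects larger than medium, and at d=.72 with b=.39 it also needs essentially no attrition.

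The consequence is limited to the mechanism aim. A reader might infer that the efficacy analyses are underpowered too; nothing here bears on H1a or H1b.

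**What to change.** In the H2 Power analysis paragraph:

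1. Replace the 80% figure with the power of the four-condition rule at N=78, and give N=98 as a sensitivity.
2. State alpha, sidedness and a numeric size for each of treatment-to-mediator, mediator-to-outcome and the total effect, with the scale on which each is expressed.
3. Add that a null H2 result will not be read as evidence against mediation at medium effect sizes.

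Optionally, as a supplementary analysis only, report a percentile-bootstrap confidence interval for each indirect effect beside the Sobel test. The decision rule need not change.

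The cost is a few lines of text and a short simulation; no new data are needed. The downside is a less favourable stated power for Aim 2.

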Participation in this study may involve a loss of privacy, but information will be handled as confidentially as possible. Participation in study assessments and any study related treatment will be documented in your electronic medical record. Research records will be labeled with a code number. The list that matches the participant name with the code number will be kept in a locked file in the research team's office. Any research records that identify the participant will be kept only as paper records in a secure VASDHS location, or as files behind the secure VASDHS computer firewall. Any presentations or publications from this information will not identify the participant. Audio recordings of treatment sessions will be stored on a VA secure server and will be accessed by [name] or her staff for the purposes of rating the psychologist's adherence to the treatment manuals. We will keep confidential all research and medical records that identify the participant to the extent allowed by law. However, there are some circumstances in which we may have to show participant information to other people. For example, the Federal Office of Human Research Protections, the General Accounting Office, the VASDHS R&D Committee, the VASDHS Institutional Review Board, and federal compliance officers may look at or copy portions of records that identify the participant.

27.b) Entry of a CPRS Research Informed Consent Note is required when subjects will be admitted as inpatients or treated as an outpatients for research and the study involves research medical care or may affect medical care.

- *If a Research consent Note is required, then a Research Progress Note should also be entered for each procedure or intervention.*
- *Scanning the Consent and HIPAA Authorization into CPRS is not required. Linking the Consent to the Research Informed Consent Note may be permitted and can be useful for trials involving the Research Pharmacy or when research will be performed in conjunction with clinical procedures.*

must be scanned into the record. Otherwise a copy of the signed I&OPI must be retained with the Investigator's research records and a copy sent to the Privacy Officer; see the ? Help for more information.

27.b1) Is entry of CPRS notes required based on the above criteria?

- CPRS notes are needed for ALL subjects
- CPRS notes are needed for SOME subjects
- CPRS notes are NOT needed for any subjects

27c) Select the VA Sensitive Information (VASI) use category

- This study does not collect or use any VASI
- This study uses but does not save, collect, copy, or record VASI
- This study does collect or record VASI

Section 27.1 VA Sensitive Information (VASI)

27.1a) For each type of VASI, indicate all that apply:

Indicate which of the following will be collected/recorded:

- Protected Health Information (PHI)
- Names
- Device identifiers and serial numbers
- E-mail addresses
- Medical record numbers
- URLs (Universal Resource Locator)
- All elements of dates (except year) or any age over 89
- Health plan beneficiary numbers
- IP Addresses (Internet Protocol)
- Telephone numbers
- Account numbers
- Biometric Identifiers including finger and voice print
- Fax numbers
- Certificate or license numbers
- Full face photographic images and comparable images
- All geographic subdivisions smaller than a state
- Vehicle ID and serial numbers including license plate numbers
- Social security numbers or scrambled SSNs (describe below)
- Other unique identifying number, characteristic, or code (describe below)

27.1b) Consent Forms and/or HIPAA Authorization

- Yes
- No

27.1c) Images with personal identifiers are used for this study (x-rays, MRI images with patient names, record numbers, dates, etc.)?

27.1d) Photos with faces or audio video recordings are used for this study.

Yes No

27.1e) Biological specimens with identifiers are used for this study.

Yes No

Section 27.2 Data Collection, Tools, and Resources

27.2a) Will any specially obtained software be used?

Yes No

27.2a1) Describe the software, and identify license requirements and the ownership of the software or license. Identify on what computer/network the software will be used (e.g., VA, VA Research/VMRF, local hard drive) and any data that will be stored in temporary files on the computer's hard drive

To assure patient confidentiality and HIPAA compliance, we will use VA--approved software, such as the VA Video Connect platform currently in use within the VA. These software packages allow standard computers with standard connections to teleconference (video and audio) in real time, using federal government tested and approved encryption. Importantly, these software encryption packages meet Federal Government Standards for encryption at a level that does not require a virtual private network (VPN; however, the software is VPN compatible) and this encryption is already Federal Information Processing Standard (FIPS) 140-2 certified and can be installed on Federal government and VA computers.

27.2b) Will any mobile devices (laptop, tablet, portable hard-drive, etc.) be used in support of this study?

Yes No

27.2b1) Provide details of the device/s. Indicate whether the device is FIPS 140-2 encryption validated and confirm that the device is listed in the VA EIL. Provide details regarding the nature of the data that will be stored or transmitted on the device and confirm whether a copy of all data will be stored on the VA network.

Participants who undergo HBVT delivery of care may use one of their own devices or computers available at the Aspire Center VA clinic. Participants will be instructed to complete treatment sessions from a private, quiet setting of their choosing. Research team staff will be available for home-based equipment set-up and training if necessary.

To assure patient confidentiality and HIPAA compliance, we will use VA-approved software, such as the VA Video Connect platform currently in use within the VA. This software package allows standard computers with standard connections to teleconference (video and audio) in real time, using federal government tested and approved encryption. Importantly, these software encryption packages meet Federal Government Standards for encryption at a level that does not require a virtual private network (VPN; however, the software is VPN compatible) and this encryption is already Federal Information Processing Standard (FIPS) 140-2 certified and can be installed on Federal government and VA

27.2c) Does the study require use of an electronic data capture system?

Yes No

27.2d) Will any other web-based applications be used (e.g., for recruitment, completing online questionnaires, or processing data)?

Yes No

27.2d1) Provide the web address, details regarding their security features, the nature of the data involved, and the research purpose. Also include a description of how VA retains a copy of the data generated using these tools.

<https://vaww.escreening.va.gov/sdc/> Escreening is available on the VA network behind the secured firewall. Each participant uses a VA computer to access and fill out questionnaires.

27.2e) Will coded data that excludes personal identifiers be used? Coded data excludes *all* HIPAA identifiers (per VHA Handbook 1605.1 Appendix B), including dates

Yes No

Section 27.3 Data Sharing and Transportation**27.3a) Does this study involve collecting, sharing or transporting any type of data outside of the local VA?**

Yes No

Section 27.4 Research Record Storage and Retention

For each type of record, indicate whether it is collected for this study

27.4a) Hardcopy records/data (includes paper, pictures, film, etc.)

Yes No

27.4a1) Identify precisely where hardcopy data will be stored to include physical site, building, and room number, etc. For each location identify whether VASI or non-sensitive information is stored at that location. For VASI, identify how the data is secured.

Hard copy data is stored in a locked filing cabinet located in a locked office, within the Aspire Center, a secured building located at [name]. Second floor,

Yes No

27.4b) Electronic study records (includes computer files, removable disk files, digital files, etc.).

Yes No

27.4b1) Identify precisely where **non-sensitive** electronic records/data will be stored to include the full map drive, network location/server name, etc., and a brief description of what data/information is stored at each location.

Information is stored behind the VA firewall in the [name] shared R drive. Participant contact information, coding sheet, and data entered into the Access database are all stored on this secured drive.

27.4b2) Identify precisely where **VASI** electronic records/data will be stored to include the full map drive, network location/server name, etc., and a brief description of what data/information is stored at each location.

If no VASI is collected or recorded for this study, simply indicate that the "Study does not collect or record VASI".

Information is stored behind the VA firewall in the [name] shared R drive. Participant contact information, coding sheet, and data entered into the Access database are all stored on this secured drive.

27.4b3) Are any of the locations described in 27.4b outside of the VA Secure Network? *Note: this includes storage on a computer local hard drive.*

Yes No

27.4c) Record Retention - VHA requires compliance with Records Control Schedule (RCS-10) for retention of electronic and hard copy records. Following study closure, these temporary records must be retained for six years and then destroyed. Longer retention may be permitted if required by other Federal regulations or requirements. Will RCS-10 requirements be followed (i.e., 6-year retention)?

I will adhere to VHA Records Control Schedule-10 requirements
 I request an exception to RCS-10 requirements

Section 27.5 Additional Privacy or Information Security Details

Provide any other privacy or information security details here.

Section 27.6 Attestations

In the event of real or suspected breach of security, the Information Security Officer, Privacy Officer, VA Police (if appropriate), and the individual's supervisor will be notified within one hour of learning of the event.

Agree Disagree

will not be allowed access to VA Sensitive Information.

Agree Disagree

Access to research sensitive information, if any, will be removed when study personnel are no longer part of the research team.

Agree Disagree

At least one copy of all study records (whether sensitive or non-sensitive) will be retained under VA control and only destroyed in compliance with the approved Records Control Schedule

Agree Disagree

The VA retains ownership of the research data. Should the investigator leave the VA, custody of the research records will be assigned to another investigator and the Research Service notified in writing, or custody of the research records will be transferred to the Research Service.

Agree Disagree

Section 28 - Protocol Association to New or Existing Project

28) Is this a new R&D Project? Before you go on to complete the *Initial Review Submission Form* (which is used for attachments), please address the association of this Protocol to an R&D Committee Project. This Protocol may represent a new R&D Project, or it may be an additional Protocol under an existing R&D Project (such as when a single grant supports multiple Protocols). Will this Protocol be submitted to the R&D Committee as a new Project?

Yes No

Section 29 - Existing Project Association

29) The associated R&D Project should already exist in the database. Identify the R&D Project(s) that correspond to this protocol.

Project Status	Proposal Number	Project Title	Principal Investigator
No Projects are Linked to this Study			

The Protocol Application is now complete for a Protocol attached to an existing Project.

Next you will go on to the Initial Review Submission Form. This form is used to collect the Application and any other needed attachments for submission to the IRB for review.

Press Save and Continue
